#### 9 DATA MANAGEMENT

# 9.1 Subject Identification

Subjects that successfully pass the screening tests and wish to participate in the study will be assigned a unique identification code (ID) using the format "XXX-YYY" where:

XXX = Institution Number, assigned by the Sponsor to each study site

YYY = Enrollment Number, assigned by the institution as each subject is enrolled in the study

In addition to the ID, each subject's initials will be used as an identifier included on documentation submitted to the Sponsor.

#### 9.2 Central Database

All study documentation will be collected and compiled in a central database. Appropriate quality control measures will be established to ensure accurate and complete transfer of information from the study documentation to the central database.

#### 9.3 **Source Documents**

Case Report Forms (CRFs) are not considered acceptable source documents. Source documents are original records in which raw data are first recorded. These may include hospital/clinic/general practitioner records, charts, for example. Source documents should be kept in a secure, limited access area. Sponsor may request copies of de-identified source document to adjudicate adverse events.

#### 9.4 **Data Collection**

Data will be collected on electronic CRFs supplied by the Sponsor or designee. The principal investigator is responsible for the prompt reporting and accuracy and completeness of all study documentation. The study data are entered into the eCRFs. Corrections made after the Investigator's review and approval must be reapproved by the Investigator.

A unique study number will be assigned to each subject. All information recorded on the CRF about the subject will be recorded with the study number on it. The main database will contain only the study number to identify the subject. The code with subject name and study number will be maintained in a secured location.

#### 9.5 **Data Processing**

Data will be entered / loaded in a validated electronic database using a clinical data management system. Visual and computer error checks will be carried out. The investigator will be queried on errors concerning completeness and consistency. An electronic audit trail system will be maintained with the clinical data management system to track all data changes in the database once the date has been entered/loaded. Regular backups of the electronic data will be performed.

#### 9.6 **Study Report**

An interim 30-day report summarizing all relevant observations will be prepared following receipt of all patient data forms. A final report will be prepared following study completion.

#### 10 STUDY ADMINISTRATION

#### 10.1 Monitoring

# **10.1.1 Monitoring Procedures**

It is the responsibility of the study sponsor to ensure that proper monitoring of this investigation is conducted. Appropriately trained monitors, appointed by the study sponsor, will complete any monitoring that is done. The monitors will ensure that the investigation is conducted in accordance with:

The signed Investigator's Agreement

- The Investigational Plan
- Appropriate laws and regulations
- Any conditions of approval imposed by the reviewing IRB and/or other regulatory agencies

The clinical study will be monitored according to the guidelines summarized below. The sponsor may choose to perform random inspections throughout the study as an element of quality assurance. Investigators shall allow auditing of their clinical investigation procedures.

A study specific monitoring plan standardizes monitoring activities across centers to ensure human subject protection and verify data integrity. The monitors shall receive study specific and protocol training prior to conducting any monitoring visits. Study monitors are selected based on their training, qualifications and experience to monitor the progress of an investigation. This study monitoring will include a site qualification, study initiation, interim, and close out visits. All study monitors will be required to follow the study monitoring plan and monitoring standard operating procedures.

The study monitoring will be done by the following Sponsor representative:

Libra Medical Inc [name] [name]

# **10.1.2** Monitoring Visit

The following factors will be taken into account when determining the frequency of the monitoring visits: subject accrual rate at each center, total number of subjects enrolled at each center, and Clinical Investigation Plan compliance at each center. It is anticipated each site will be monitored at least once upon the completion of the 30-day follow-up visits for all enrolled subjects at the study site. Monitors will require direct access to subjects' medical records pertinent to the study (and study inclusion criteria), study management documents, regulatory documents and Subject Informed Consent documents, as well as other potential applicable records not listed here.

Monitors may ensure the clinical investigators have and continue to have staff and facilities to conduct the clinical investigation safely and effectively. Monitors may conduct the following monitoring activities throughout the study:

• Verification that the current IRB-approved informed consent was signed and dated by each subject prior to participating in the study required procedures.

- Verification of documentation in the subject's record that informed consent was signed prior to initiation of the study procedures and that a copy of the signed and dated consent was provided to the subject.
- Source documentation verification by reviewing the CRFs against source documentation for accuracy and completeness of information.
- Verification that the investigation is conducted according to the Clinical Investigation Plan, Instructions for Use and, all malfunctions/ IFU deficiencies are reported as required.
- Verification that subjects met study enrollment criteria.
- Verification that study deviations are documented and reported.
- Verification that the procedures for recording and reporting adverse events to the sponsor are followed.
- Ensuring proper error correction.
- Verification of training documentation of all study personnel participating in study related activities.
- Reviewing all correspondence and regulatory documents, including confirmation of IRB-approved Clinical Investigation Plan or amendments.
- Resolution of outstanding issues and completion of assigned tasks will be documented by the monitors.

Each monitoring visit will be documented via a monitoring report and follow-up letter. The follow-up letter shall be sent to the Investigator to document issues identified, corrective actions and if applicable preventative actions. At subsequent visits any issues resolved shall be documented in this letter to demonstrate resolution.

# 10.1.3 Study Closure

Study closure is defined as a specific date that is determined by study completion and/or regulatory requirements have been satisfied per the Clinical Investigation Plan (CIP) and/or by decision of the Sponsor or FDA. Study closure visits will be conducted at all enrolling clinical sites in order to review record retention requirements with site personnel. A telephone contact may take the place of a study closure visit if appropriate (e.g., low subject enrollment, recent monitoring visit, etc.) Monitoring visits will be conducted by trained monitors and designees. The Monitoring Plan identifies the frequency of monitoring and training requirements of the monitors.

# 10.2 Device Accountability

Access to investigational devices shall be controlled and used only in the clinical investigation and according to the Protocol. Each site will be responsible for tracking the receipt and disposition of all investigational devices. All unused devices must be returned to the Sponsor at the end of the study.

The principal investigator or an authorized designee shall keep records documenting the receipt, use, return, and disposal of the investigational device, which shall include:

- The date of receipt
- Identification of each investigational device (serial or lot number)
- The date or dates of use
- Subject identification
- Date of return of unused, expired, or malfunctioning investigational device, if applicable
- The Investigator must explain in writing the reasons for any discrepancy noted in device accountability.

## 11 DEFINITION OF ADVERSE EVENT(S)

For purposes of this study, an adverse event (AE) is defined as any adverse change (i.e., de novo or pre-existing condition) from the subject's baseline medical condition(s) occurring during the course of the study. Adverse events (AE) are any untoward medical occurrence, unintended disease or injury, or untoward clinical signs (including abnormal laboratory findings) in subjects, whether or not related to the investigational medical device. For the purpose of AE documentation, the start of the course of the study is defined as any time after the treatment has been initiated. All AE's will be recorded in the CRF whether considered procedure-related or not, and will be classified as described in this section.

Pre-existing conditions will not be reported as an AE unless there is an adverse change in that condition. Any AE which resolved and then recurred will be reported as a separate AE.

An AE may be volunteered spontaneously by the subject or discovered as a result of questioning or physical examination by an investigator or study staff.

Elective procedures for a pre-existing condition (that has not worsened) are not considered AEs. Non-cardiovascular abnormal laboratory values will not be considered AEs unless:

- 1) The PI determines that the value is clinically significant,
- 2) The abnormal laboratory value required intervention, or
- 3) The abnormal laboratory value required subject termination from the trial.

All adverse events, regardless of relationship to the device, must be recorded, as applicable, on the case report forms provided. Adverse events that occur during this study should be treated by established standards of care, to protect the life and safety of the subjects.

Adverse events shall be assessed and documented at the time of the procedure and at all study follow-up visits. Each investigator shall provide source documentation as requested by the Sponsor to facilitate reporting and adjudication of these events.

## 11.1 Serious Adverse Events

An adverse event is considered a Serious Adverse Event (SAE) that:

- a) led to death
- b) led to a serious deterioration in the health of the subject, that either resulted in
  - 1) a life-threatening illness or injury, or
  - 2) a permanent impairment of a body structure or a body function, or
  - 3) in-patient hospitalization or prolongation of existing hospitalization, or
  - 4) a medical or surgical intervention to prevent permanent life-threatening illness or injury or permanent impairment to body structure or a body function.

# 11.2 Device Relationship

Determination whether there is a reasonable possibility that a study product or device caused or contributed to an AE is to be determined by the Investigator and recorded on the appropriate CRF form. Determination should be based on assessment of temporal relationships, biologic plausibility, association (or lack of association) with underlying disease and presence (or absence) of a more likely cause.

# 11.3 Unanticipated Adverse Device Effect

An unanticipated adverse device effect (UADE) is any serious adverse effect on the health or safety of a subject, any life-threatening problem or death caused by, or associated with a device, if such effect, problem, or death was not previously identified in nature, severity, or degree of incidence in the investigational plan (e.g., ICF, Study Protocol, Instructions for Use (IFU), publications, etc.), or any other unanticipated serious problem associated with a device that relates to the rights, safety, or welfare of subjects.

If an unanticipated adverse effect associated with the investigational device occurs, the investigator shall notify the Sponsor and the IRB/EC as soon as possible.

The Sponsor will investigate the event and notify the FDA and all other participating IRBs and investigators. Should the Sponsor determine that an unanticipated adverse effect presents an unreasonable risk to all participating subjects, the Sponsor will suspend the clinical investigation and notify all participating investigators, IRBs/EC, country regulatory bodies and FDA.

# 11.4 Adverse Event Reporting

The signs, symptoms and sequelae of an underlying AE should not be reported as separate AEs. All AEs must be recorded on a CRF. All AEs also must be described by (a) duration (start and resolution dates); (b) adjudicated for severity; (c) relationship to the study device; (d) action taken to resolve the event; (e) outcome of the event; and (f) whether or not such event is considered to

be serious. Additional information, such as procedural notes, treatment notes, or a signed clinical summary, may be required as supporting documentation for the reported AE.

Pre-existing medical conditions or symptoms occurring prior to the start of the atherectomy procedure should not be reported as adverse events. In the situation where there is a worsening of a pre-existing medical condition or symptom due to a study related procedure, an adverse event should be reported.

For any adverse event that is ongoing at the time of the initial report, periodic follow-up information is required until the adverse event is resolved or is judged to be chronically stable. The site should submit relevant follow-up information related to the adverse event as soon as it is available.

Depending upon the nature and seriousness of the adverse event, the sponsor or designee may request the Investigator to provide copies of the subject's medical records (such as the subject's laboratory tests and hospital records, Investigator summaries, etc.) to document the adverse event.

The Investigator will report all serious adverse events, including unanticipated adverse device effects, to the IRB according to the IRB requirements. A copy of this IRB communication should be sent to the Sponsor. In case of an unanticipated adverse device effect occurred, the investigator must report to the Sponsor within 10 working days of the site first becoming aware of the event.

Within 10 working days of notification, the Sponsor will report all unanticipated adverse device effects to the appropriate authority, all participating investigators, and all reviewing IRBs. The Sponsor will ensure that safety reporting for the study is conducted in compliance with all pertinent requirements and regulations.

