#### 1 BACKGROUND AND RATIONALE

Atherosclerosis causes symptomatic disease primarily in the coronary arteries, the peripheral arteries of the lower extremities, and the extra-cranial carotid arteries. Of the three, peripheral artery disease (PAD) is probably the most under-diagnosed and least aggressively managed, despite its strong association with cardiovascular disease (CVD) and death. PAD is chronic occlusive artery disease of the lower extremities and a strong surrogate marker for atherosclerosis in the heart, kidneys, and brain. PAD is associated with a 60% incidence of coronary or cerebrovascular disease. About 90% of patients with symptomatic PAD have coronary artery disease (CAD) as well. The disease can have devastating effects on quality of life and survival, with mortality around 30% in 5 years, 50% in 10 years and 75% in 15 years. Overall, CVD causes death in 75% of PAD patients.

Most common among elderly people, diabetics, and smokers, PAD afflicts an estimated 8-12 million people in the United States alone. Its prevalence is likely to increase greatly in the next several decades as the risk factors of diabetes, smoking, hypertension, dyslipidemia and cardiovascular incidence increase.

Classic symptoms of PAD include intermittent claudication (IC), defined as leg muscle pain or weakness that occurs during walking and subsides with rest. The exercise-induced symptoms are distal to the obstruction in the artery that supplies the leg. Rest pain in the toes or foot indicates that arterial blood flow cannot meet the needs of resting metabolism. The resulting critical limb ischemia (CLI) can progress to ulceration or gangrene in the toes, ankle, heel, or leg, often necessitating amputation.

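### Section 11.4 ties reporting of a worsened pre-existing condition to the study procedure, while Section 11 requires it whatever the cause, so the adverse event record may be incomplete

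*Combined protocol and SAP*

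**What the plan says.** Section 11 sets the definition without any causal condition. An AE is "any adverse change (i.e., de novo or pre-existing condition) from the subject's baseline medical condition(s) occurring during the course of the study". It then says: "Pre-existing conditions will not be reported as an AE unless there is an adverse change in that condition". On recording it is explicit twice: "All AE's will be recorded in the CRF whether considered procedure-related or not", and "All adverse events, regardless of relationship to the device, must be recorded, as applicable, on the case report forms provided".

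Section 11.4, which governs reporting, starts from the opposite side: "Pre-existing medical conditions or symptoms occurring prior to the start of the atherectomy procedure should not be reported as adverse events". The sentence that follows calls for an AE report where there is "worsening of a pre-existing medical condition or symptom due to a study related procedure". The same section also requires all AEs to go on a case report form.

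Relationship has its own step. Sections 11.2 and 11.5.3 have the investigator grade each AE against the device once it exists. Section 12.2 then gives one independent physician the events that the principal investigator or the sponsor may regard as serious or device related.

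**The concern.** Section 11 asks whether the subject got worse. Section 11.4 asks whether the subject got worse because of the procedure. The second question puts a causality judgement by the treating investigator ahead of recording, where Section 11 puts it afterwards.

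Every subject enters with peripheral artery disease, so worsening limb symptoms are the events most easily put down to natural progression. Two sites could follow different sections, each believe it complied, and return AE data that are not comparable. Section 8 plans only descriptive summaries in up to 10 subjects, so the value of the safety result rests on complete capture.

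**Working it through.** The protocol states no figure on this point, so there is none to reproduce. The check is a comparison of the text, followed by an illustration of scale.

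**1. Do the two rules conflict?** Take a subject whose angina or claudication worsens after the procedure, and whose investigator attributes this to disease progression.

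- Under Section 11 it is an adverse change in a pre-existing condition, so it is an AE and is recorded.
- Under 11.4 the default is not to report pre-existing conditions, and the one stated exception is not met. Read as a default with a single exception, it is not reported.

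The requirement in 11.4 to record all AEs does not settle this, because the question is whether this worsening counts as a reportable AE.

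**2. Would a later step recover the event?**

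- *Relationship grading (11.2, 11.5.1, 11.5.3).* It applies to recorded AEs and concerns the device. No scale for relationship to the procedure is given, so a judgement that worsening was not due to the procedure need leave no trace.
- *Adjudication (12.2).* The adjudicator has no stated task of looking for unreported events.
- *Monitoring (10.1.2).* At least one visit per site is anticipated, after the 30-day visits. Source verification and checks that reporting procedures were followed are listed as activities monitors may carry out. An omission that agrees with 11.4 could pass.
- *Scheduled assessments (6.7, 6.8).* Rutherford class, ABI, duplex and VascuQoL would show limb worsening as effectiveness data, though not as an AE. Apart from physical examination and vital signs, no scheduled follow-up assessment is aimed at worsening cardiac disease.

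**3. Which MAE components (5.1) are exposed?**

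| Component | Other route or reason | Exposed to the 11.4 condition? |
|---|---|---|
| Cardiovascular death | All deaths reported whatever the cause (11.7, Table 12-1) | No |
| Dissection, perforation, pseudoaneurysm | Confirmed by angiography; core laboratory reads all angiograms (12.1) | No |
| Distal embolization | Exclusion criterion 13 rules it out at entry, so it would be new | No, in practice |
| Myocardial infarction | Must be newly diagnosed, so it is a new event | Not plainly |
| Target lesion revascularization | Also a secondary endpoint, verified by the core laboratory (5.3.2) | Little |
| Unplanned major amputation | No imaging or core laboratory route; physical examination at follow-up | Yes, the nearest case |

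Two qualifications apply. CK-MB, which defines infarction, is not named in 6.4, 6.6 to 6.8 or Table 6-1, so its detection also leans on the site; but that does not arise from 11.4. For revascularization, the core laboratory verifies a diagnosis and is not described as searching for cases.

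**4. Scale.** Input: up to 10 subjects (4.2). Freedom from MAE = (10 − x)/10.

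- x = 0: 10/10 = 100%
- x = 1: 9/10 = 90%
- Difference: 10 percentage points per subject whose only MAE is missed.

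For context, exact 95% intervals for the MAE rate, which the protocol does not plan, are 0 to 1 − 0.025^(1/10) = 0.3085 (about 31%) for 0/10, and 0.25% to 44.5% for 1/10 (Clopper-Pearson). The 10 points hold if an event is missed. They are not an estimate of expected bias.

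**The case against.** The strongest reply is that 11.4 never says *only*. Its do-not-report sentence concerns conditions present before the atherectomy starts, the same section requires all AEs on a form, and Section 11 holds the definition and says twice that relationship is irrelevant to recording. An investigator who withheld a worsening on the strength of 11.4 would still breach Section 11. This stands: the text is a conflict between two sections and not a clear licence to withhold. It does not remove the conflict, because a site that reads the reporting section on its own has a natural reason to omit the event.

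A reader might infer that ischemic and cardiac MAEs in general can be filtered out before adjudication. The component table does not support that.

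A reader might also take "About 90% of patients with symptomatic PAD have coronary artery disease (CAD) as well" to mean that about 9 of 10 subjects are exposed on the cardiac side. That sentence is a background population statement. The trial excludes unstable coronary disease and infarction within 2 months (exclusion criteria 9 and 11), and having coronary disease is not the probability of an unreported event.

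The related serious AE endpoint (5.3.1) also needs care. An event that the investigator puts down to progression would probably be classed as unrelated by that investigator even if recorded. The omission matters there only where the sponsor or the adjudicator would have disagreed, and they cannot disagree about an event they never see.

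Finally, the limit on what reaches the adjudicator comes from 12.2 as much as from 11.4. Correcting 11.4 alone would leave it in place.

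**Conclusion.** The inconsistency is real and should be corrected. As written, 11.4 attaches a causal condition to reporting that Section 11 rules out. The likely loss is non-fatal worsening of limb or cardiac disease attributed to natural progression. It falls mainly on the AE and serious AE listings and on the pool of events available for adjudication as related, and to a lesser extent on the 30-day MAE composite.

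This rests on two assumptions: that some sites would read 11.4 as a default with one exception, and that nothing outside these documents, such as form completion instructions, already resolves the conflict. The documents do not support a claim that the primary safety result is biased by a known amount.

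**What to change.** In 11.4, delete the closing six-word causal condition from the sentence on worsening, and align the sentence with Section 11. For example: *Any worsening of a pre-existing condition or symptom after the start of the procedure is recorded as an adverse event, and its relationship is assessed afterwards.*

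In 12.2, add that every event that could be an MAE component goes to the independent adjudicator whatever the investigator's opinion on causality. Without this, the restriction on what is adjudicated remains.

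The cost is two short text edits, slightly more AE forms and slightly more adjudication. With at most 10 subjects the extra load is small. No endpoint, visit or analysis changes.
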